## **8.1. Efficacy Assessments**

### **8.1.1. Rater Qualifications**

Clinical evaluations of AD will be performed by an experienced and certified physician, dermatologist, or medical professional. The evaluator must have received documented training to conduct the protocol AD specific clinical evaluations prior to performing these evaluations. To assure consistency and reduce variability, the same evaluator must assess all clinical evaluation of atopic dermatitis for any individual participant throughout the study; a backup experienced and qualified, protocol trained evaluator will only be allowed and documented in case of emergency or special situation when the designated evaluator is unable to perform the evaluation. Identity (eg, initials) of the evaluator will be captured on the source documentation (eg, scale worksheet).

### **8.1.2. Calculation of Treatable %Body Surface Area (BSA)**

The treatable %BSA is defined as the percentage of the participant's total BSA that is AD involved, excluding the scalp, and will be calculated at times specified in the [SoA](#). The treatable %BSA should be evaluated based on all AD lesions present on the day of the visit, excluding the scalp. Score 0 in the ISGA definition will not be evaluated as BSA while Score 1-4 will be.

To estimate the treatable %BSA, the investigator or designee will use "handprint method", by which the area represented by the palmar (i.e., outstretched) surface of the participant's hand with all five digits adducted together is approximately 1% of the participant's BSA, regardless of the participant's age.

### **8.1.3. Investigator's Static Global Assessment (ISGA)**

The ISGA is a 5-point scale (0-4), reflecting a global assessment of AD severity based on erythema, induration/papulation, and oozing/crusting ([Table 1](#)). ISGA will be assessed at times specified in the [SoA](#) to characterize participants' overall disease severity across all treatable AD lesions (excluding the scalp). ISGA should be completed prior to assessment of Regional ISGA-Face and EASI, whenever possible. The assessment will be a static evaluation without regard to the score at a previous visit.

**Table 1. Investigator’s Static Global Assessment**

Score	Grade	Definition
0	Clear	Minor residual hypo/hyperpigmentation; no erythema or induration/papulation; no oozing/crusting
1	Almost Clear	Trace faint pink erythema, with barely perceptible induration/papulation and no oozing/crusting
2	Mild	Faint pink erythema with mild induration/papulation and no oozing/crusting
3	Moderate	Pink-red erythema with moderate induration/papulation with or without oozing/crusting
4	Severe	Deep or bright red erythema with severe induration/papulation and with oozing/crusting

#### 8.1.4. Regional ISGA-Face

Severity of AD on the face will be assessed by evaluating the severity of all lesions occurring within that body region. The Regional ISGA-Face score will be assessed only for participants who completed Study C3291032 and had AD in face at Day 1 Visit of Study C3291032. At every scheduled visit, the Regional ISGA score will be documented for the face regardless of the presence or absence of AD in face. The Regional ISGA-Face assessment should use the scale in Table 1.

The assessment will be a static evaluation without regard to the score at a previous visit.

#### 8.1.5. Eczema Area and Severity Index (EASI)

The EASI quantifies the severity of a participant’s AD based on both severity of lesion clinical signs and the percent of BSA affected. EASI is a composite scoring of the degree of erythema, induration/papulation, excoriation, and lichenification (each scored separately) for each of 4 body regions, with adjustment for the percent of BSA involved for each body region and for the proportion of the body region to the whole body.

The EASI score can vary in increments of 0.1 and range from 0.0 to 72.0, with higher scores representing greater severity of AD. Since the scalp will be excluded from the EASI assessment in this study, the maximum possible score will be less than 72.0.

The EASI will be assessed at times specified in the [SoA](#).

**Lesion Severity by Clinical Signs:** The basic characteristics of AD lesions (erythema, induration/papulation, excoriation, and lichenification) provide a means for assessing the severity of lesions. Assessment of these 4 main clinical signs is performed separately for 4 body regions: head and neck, upper limbs, trunk (including axillae and groin) and lower limbs (including buttocks). Average erythema, induration/papulation, excoriation, and lichenification are scored for each body region according to a 4-point scale: 0 = absent; 1 = mild; 2 = moderate; 3 = severe. Morphologic descriptors for each clinical sign severity score are shown in [Table 2](#).

**Table 2. Clinical Sign Severity Scoring Criteria for EASI**

Score		Description
Erythema (E)		
0	Absent	None; may have residual discoloration (post-inflammatory hyperpigmentation and/or hypopigmentation)
1	Mild	Light pink to light red
2	Moderate	Red
3	Severe	Deep, dark red
Induration/Papulation (I)		
0	Absent	None
1	Mild	Barely palpable to slight, but definite hard thickened skin and/or papules
2	Moderate	Easily palpable moderate hard thickened skin and/or papules
3	Severe	Severe hard thickened skin and/or papules
Excoriation (Ex)		
0	Absent	None
1	Mild	Slight, but definite linear or picked scratch marks or penetrating surface injury
2	Moderate	Moderate linear or picked scratch marks or penetrating surface injury
3	Severe	Severe linear or picked scratch marks or penetrating surface injury
Lichenification (L)		
0	Absent	None
1	Mild	Barely perceptible to slight, but definite thickened skin, fine skin markings, and lichenoid scale
2	Moderate	Moderate thickened skin, coarse skin markings, and coarse lichenoid scale
3	Severe	Severe thickened skin with very coarse skin markings and lichenoid scale

Note: The EASI will exclude scalp from the assessment/scoring.

**Percent BSA with Treatable AD:** The number of handprints of AD skin in a body region can be used to determine the extent (%) to which a body region is involved with AD (Table 3). The handprint as a unit is defined by the area represented by the palmar (ie, outstretched) surface of the participant's hand with all 5 digits adducted (not spread apart) together equaling approximately 1% of the participant's BSA, regardless of the participants age.

**Table 3. Handprint Determination of Body Region Surface Area**

Body Region	Total Number of Handprints in Body Region a	Surface Area of Body Region Equivalent of One Handprint	Total Number of Handprints in Body Region a		Surface Area of Body Region Equivalent of One Handprint	
			≥8 years of age		<8 years of age	
Head and Neck	10	10%	20	5%	20	5%
Upper Limbs	20	5%	20	5%	20	5%
Trunk (including axillae)	30	3.33%	30	3.33%	30	3.33%
Lower Limbs (including buttocks)	40	2.5%	30	3.33%	30	3.33%

a. The number of handprints will be for the entire body region; these values will not be adjusted for exclusion of scalp from the BSA assessment.

The extent (%) to which each of the 4 body regions is involved with AD is categorized using a nonlinear scaling method to derive a numerical area score according to the BSA scoring criteria (Table 4).

**Table 4. Eczema Area and Severity Index (EASI) Area Score Criteria**

Treatable Percent Body Surface Area with Atopic Dermatitis in a Body Region	Area Score
0%	0
>0% to <10%	1
10% to <30%	2
30% to <50%	3
50% to <70%	4
70% to <90%	5
90% to 100%	6

**Body Region Weighting:** Each body region is weighted according to its approximate percentage of the whole body (Table 5).

**Table 5. Eczema Area and Severity Index (EASI) Body Region Weighting**

Body Region	Body Region Weighting	
	≥8 years of age	<8 years of age
Head and Neck	0.1	0.2
Upper Limbs	0.2	0.2
Trunk (including axillae and groin/genitals)	0.3	0.3
Lower Limbs (including buttocks)	0.4	0.3

In each body region, the sum of the Clinical Signs Severity Scores for erythema, induration/papulation, excoriation, and lichenification is multiplied by the Area Score and by the Body Region Weighting to provide a body region value, which is then summed across all 4 body regions resulting in an EASI score as described in Equation 1 and Equation 2:

**Equation 1 (participants aged ≥8 years old):**  $EASI = 0.1Ah(Eh+Ih+Exh+Lh) + 0.2Au(Eu+Iu+Exu+Lu) + 0.3At(Et+It+Ext+Lt) + 0.4Al(El+Il+Exl+Ll)$

**Equation 2 (participants aged <8 years old):**  $EASI = 0.2Ah(Eh+Ih+Exh+Lh) + 0.2Au(Eu+Iu+Exu+Lu) + 0.3At(Et+It+Ext+Lt) + 0.3Al(El+Il+Exl+Ll)$

A = Area Score; E = erythema; I = induration/papulation; Ex = excoriation; L = lichenification; h = head and neck; u = upper limbs; t = trunk; l = lower limbs.

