- g. For studies enrolling pediatric participants, it is the opportunity to assess changing potential to father/bear children and allows for implementing contraception and pregnancy testing as children mature physically and behaviorally during conduct of the study.
- h. Study coordinator or specified designee will contact IRT to register the visit and, if applicable, obtain the next investigational product tube(s) assignment.
- i. Participant who will start “On-treatment Cycle” from Enrollment Visit.
- j. At home dosing by participant or his/her parent/legal guardian. Investigational product application BID through the evening before the day of visit. After the procedure/assessment of the visit, the participant or his/her parent/legal guardian can apply the investigational product, if applicable.
- k. In the event the scheduled Start Day of the next treatment cycle visit does not fall exactly on the scheduled date, the participant or his/her parent/legal guardian will be instructed to continue investigational product application BID through the evening before the actual visit date.
- l. Performed only for those participants completing a previous On-Treatment Cycle (e.g., Previous “On-treatment” and continue “On-treatment”, or previous “On-treatment” and initiate “Off-treatment”).
- m. The ISGA should be completed prior to Regional ISGA-face and EASI assessments, whenever possible.
- n. Peak Pruritus NRS will be completed by participants ≥12 years of age at the time of signing the ICD in the prior study, Patient Reported Itch Severity Scale will be completed by participants ≥6 years and <12 years at the time of signing the ICD in the prior study, and Observer Reported Itch Severity Scale will be completed by the observers (caregivers of participants) for participants <6 years of age at the time of signing the ICD in the prior study.
- o. Only for participants who completed study intervention for Study C3291032 and had AD in face at Day 1 Visit of Study C3291032.
- p. Performed to remind the participants initiating “Off-treatment Cycle” to bring back dosing diary which records concomitant medication usage.
- q. PK blood sampling will be conducted at the selected study sites in participants aged between 2 years old and 11 years old at the time of signing the ICD in Study C3291032. The date and time for most recent dose (last dose in C3291032 study) will be collected.

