### 8.1.7. Patient/Observer Reported Outcomes

The Patient/Observer Reported Outcomes questionnaires in this study include Peak pruritus NRS/Patient Reported Itch Severity Scale/Observer Reported Itch Severity Scale. They will be performed at the time points defined in the [SoA](#). The age cut-offs are based on the age at Screening visit/informed consent/assent in the prior study.

On study visit days, participants or observers (ie, the one who provides the information to complete the questionnaires other than participant, eg, his/her parent/legal guardian/other caregiver) should complete the patient/observer reported outcomes at the clinic prior to any procedures being performed. The one who completed the questionnaires should be captured and stored in the database and available for analysis. It's preferred that all observer reported outcomes for a given participant are completed by same individual throughout the study.

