#### 8.1.7.1. Pruritus Assessment

Participants will be asked to assess their worst itch or scratching due to AD over the past 24 hours.

- Peak Pruritus NRS is an 11-point scale and must be completed by participants ≥12 years of age at the time of signing the ICD in the prior study.
- Patient reported Itch Severity Scale is a 5-point scale must be completed by participants ≥6 years and <12 years at the time of signing the ICD in the prior study.

- Observer reported Itch Severity Scale is an 11-point scale and must be completed by the observers (caregivers of participants) for participants <6 years of age at the time of signing the ICD in the prior study.

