1. VERSION HISTORY

Table 1. Summary of Changes

Version/ Date	Associated Protocol Amendment	Rationale	Specific Changes
1 4 Aug 2020	Original 20 May 2020	N/A	N/A
2 7 Jan 2021	Original 20 May 2020	Study termination	Updated the following analyses due to the small sample size and the short exposure period. 6.4. Subset Analyses 6.5.3. Study Treatment Exposure 6.5.4. Concomitant Medications and Nondrug Treatments 6.6.1. Adverse Events

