3.4. Baseline Variables

For the purpose of analysis of efficacy and patient/observer reported outcomes endpoints, the baseline values are defined as the baseline values from the participant's parent phase 3 study.

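### Does the missing reference date for the EASI age band (under 8 versus 8 and over) undermine the EASI change endpoints?

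*Protocol*

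**What the plan says.** Protocol Section 8.1.5 gives two scoring rules. For "Equation 1 (participants aged ≥8 years old" the region weights are 0.1 head and neck, 0.2 upper limbs, 0.3 trunk and 0.4 lower limbs. For "Equation 2 (participants aged <8 years old" they are 0.2, 0.2, 0.3 and 0.3. Table 3 also changes at age 8: the head and neck count as 10 handprints from age 8 and 20 below it, the lower limbs as 40 and 30. On the use of Table 3 the protocol says "The number of handprints of AD skin in a body region can be used to determine the extent". No date is attached to the age in any of these places.

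Elsewhere age is dated. For the itch scales, Protocol Section 8.1.7 says "The age cut-offs are based on the age at Screening visit/informed consent/assent in the prior study", and Section 8.1.7.1 repeats the rule for each scale ("at the time of signing the ICD in the prior study"). PK sampling is for children "aged between 2 years old and 11 years old at the time of signing the ICD in Study C3291032" (Schedule of Activities, note q).

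Change in EASI is measured from the parent study: in SAP Section 3.4 "the baseline values are defined as the baseline values from the" parent phase 3 study. SAP Sections 6.3.1.1 to 6.3.1.3 summarise percent change, EASI50 and EASI75 without an age rule. Section 6.4 adds percent change by age group, including 2-11. The version history attributes SAP version 2 to study termination: "Updated the following analyses due to the small sample size and the short exposure period".

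**The concern.** A percent change means something only if both scores come from the same formula. Read as age at the visit, the text would let a child who is 7 at the parent-study baseline be scored with Equation 2 then and Equation 1 later. Part of the apparent change would reflect the birthday and not the skin. The itch-scale rule does not settle this, because it sits under patient- and observer-reported outcomes, while EASI is rated by the investigator. The contrast suggests that the authors saw the need for a fixed age in one place and missed it in another.

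At stake are the percent change in EASI and the EASI50 and EASI75 rates. In a small sample, one child whose status flips moves a responder rate by 3 to 10 percentage points (1/30 to 1/10, taking n = 30 to 10 as an assumption).

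**Working it through.** **Plan's own figure.** The maximum is the sum over regions of weight × 6 × 12. The weights sum to 1.0 in both equations, so both give 72.0, the upper limit stated in Section 8.1.5 before the scalp is excluded.

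**Who could cross.** Only entrants from C3291032, since C3291031 enrols children under 24 months. Parent-study Day 29 serves as Day 1 here, so baseline to Week 52 is 28 + 364 = 392 days, or 1.07 years. A child must be about 6.9 to just under 8 at baseline.

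**Unchanged skin, area scores unchanged, formula switched.** Area score 2 and sign sum 6 in each affected region:

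| Regions affected | Equation 2 | Equation 1 | Apparent change |
|---|---|---|---|
| Head and neck | 0.2×2×6 = 2.4 | 0.1×2×6 = 1.2 | -50.0% |
| Lower limbs | 0.3×2×6 = 3.6 | 0.4×2×6 = 4.8 | +33.3% |
| Head and neck, upper limbs | 4.8 | 3.6 | -25.0% |
| Upper and lower limbs | 6.0 | 7.2 | +20.0% |
| All four alike | 12.0 | 12.0 | 0% |

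**Unchanged skin, handprints fixed, disease in all four regions.** With 1 to 8 whole handprints per region (8⁴ = 4,096 combinations) and equal sign sums, Table 3 and Table 5 both switch. The answer depends on how Table 3 is read:

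- Printed 3.33% per handprint: -8% to +15%, with 90% of combinations within ±10%.
- Exact thirds: -27% to +15%, with 81% within ±10%.

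The longer lower tail comes from three handprints on the legs. That is 9.99% (area score 1) with the printed figure and exactly 10% (area score 2) with thirds.

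**Can responder status flip when there is true change?** Yes, in either direction.

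- Head and neck area score 2 (two handprints, the same score under both columns) with sign sum 6 to 4; upper limbs area score 1 with sum 4 to 2. Baseline: 0.2×2×6 + 0.2×1×4 = 3.2. Follow-up by Equation 2: 1.6 + 0.4 = 2.0, a true -37.5%. Follow-up by Equation 1: 0.8 + 0.4 = 1.2, read as -62.5%. EASI50 is gained.
- Four handprints in every region, sign sum 8 to 4. All area scores are 2, except head and neck, which becomes 3 under the older column. Baseline: 2×8×1.0 = 16.0. Same formula: 8.0, a true -50.0%. Switched: 4×(0.1×3 + 0.9×2) = 8.4, read as -47.5%. EASI50 is lost.
- The same skin with sign sum 8 to 2: true -75.0%, read as 4.2/16.0 - 1 = -73.8%. EASI75 is lost.

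**How many children.** The documents give no age distribution. Assume ages spread evenly over ten years (2 to 11), so the share crossing is follow-up in years divided by 10.

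- Planned study: 1.07/10 = 10.7%. If 20% to 75% of the 130 entrants aged 2 and over are aged 2 to 11, then 130 × 0.20 × 0.107 = 2.8 to 130 × 0.75 × 0.107 = 10.4 children.
- After termination: 91 days gives 2.5%. The 232 days from the protocol (20 May 2020) to SAP version 2 (7 January 2021) gives 6.4%. Actual follow-up is not stated, so these are working values and not bounds. Per 10 enrolled: 10 × 0.20 × 0.025 = 0.05 to 10 × 0.75 × 0.064 = 0.48. Per 30 enrolled: 0.15 to 1.44.

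**The case for a change.** The strongest case for acting is that the omission is real, the consequence follows arithmetically, and one derivation sentence would close it. SAP version 2, written because of the termination, still keeps percent change in EASI, EASI50 and EASI75, and it keeps the 2-11 subgroup that contains the boundary. Exploratory results also need a single defined derivation, and sites, programmers and the parent studies could in principle differ.

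The gap and the arithmetic stand. What does not follow is that the plan is wrong. Harm needs several things together: age updated at each visit, a child crossing 8 within the observed follow-up, and then either disease concentrated in the head and neck or legs, or a true response close to a cut-off. Nothing in the documents points to the first. The baseline score, and for C3291032 entrants the enrolment score as well, come from the parent study. Its age convention is not in these documents, so no inconsistency with it can be shown. For a study already terminated, writing the convention down would have little or no effect on scoring at sites.

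**Conclusion.** No change to the plan is called for. This is missing detail that an analyst fills sensibly: one formula per participant, set by age at entry, is the natural choice for a change score and matches how the protocol treats age for the itch scales and PK sampling. On that reading unchanged skin gives 0% change and the concern disappears.

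On the less likely reading the distortion for an affected child could be large (-50% to +33% with single-region disease). It is usually modest with disease in all four regions: -8% to +15% with the printed handprint percentages, -27% to +15% with exact thirds. The expected number of such children is about 0.05 to 0.5 per 10 enrolled, possibly none, given an even age spread over 2 to 11, 20% to 75% of entrants in that range, and about 3 to 7.6 months of follow-up. The primary safety endpoint is untouched, treatment cycles follow ISGA and not EASI, and no hypothesis is tested on EASI. The conclusion would weaken only if scores had in fact been derived by age at visit and a participant had crossed age 8; neither can be determined from the documents.

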### 8.1.6. Body Site Checklist for Atopic Dermatitis

A checklist of body areas currently affected by AD will be completed at times specified in the [SoA](#). Location of skin lesions will be selected from a pre-specified list of body locations.

Any new lesion should be recorded and updated in the checklist. Study site staff (or the investigator) will determine whether a new AD lesion is reported as an AE or as part of the underlying disease based on medical judgement. The AD lesion checklist will be recorded in the participant's source documents and data entered onto the CRF.

### 8.1.7. Patient/Observer Reported Outcomes

The Patient/Observer Reported Outcomes questionnaires in this study include Peak pruritus NRS/Patient Reported Itch Severity Scale/Observer Reported Itch Severity Scale. They will be performed at the time points defined in the [SoA](#). The age cut-offs are based on the age at Screening visit/informed consent/assent in the prior study.

On study visit days, participants or observers (ie, the one who provides the information to complete the questionnaires other than participant, eg, his/her parent/legal guardian/other caregiver) should complete the patient/observer reported outcomes at the clinic prior to any procedures being performed. The one who completed the questionnaires should be captured and stored in the database and available for analysis. It's preferred that all observer reported outcomes for a given participant are completed by same individual throughout the study.

#### 8.1.7.1. Pruritus Assessment

Participants will be asked to assess their worst itch or scratching due to AD over the past 24 hours.

- Peak Pruritus NRS is an 11-point scale and must be completed by participants ≥12 years of age at the time of signing the ICD in the prior study.
- Patient reported Itch Severity Scale is a 5-point scale must be completed by participants ≥6 years and <12 years at the time of signing the ICD in the prior study.

- Observer reported Itch Severity Scale is an 11-point scale and must be completed by the observers (caregivers of participants) for participants <6 years of age at the time of signing the ICD in the prior study.

## **8.2. Safety Assessments**

Planned time points for all safety assessments are provided in the [SoA](#). Unscheduled clinical laboratory measurements may be obtained at any time during the study to assess any perceived safety issues.

### **8.2.1. Physical Examinations**

A complete physical examination will include, at a minimum, assessments of the cardiovascular, respiratory, gastrointestinal, and neurological systems. In addition, an assessment will be made of the condition of all AD-involved skin. Weight for participants aged 18 years old or older and height and weight for participants aged under 18 years old will also be measured and recorded.

Investigators should pay special attention to clinical signs related to previous serious illnesses.

For measuring weight, a scale with appropriate range and resolution is used and must be placed on a stable, flat surface. Participants must remove shoes, bulky layer or clothing, and jackets so that only light clothing remains. They must also remove the contents of their pockets and remain still during measurement of weight.

